6.20.5 Physical Examination

Abnormal findings in physical examination will be recorded as medical history for pre- dose assessments and as adverse events for post-dose assessments.

7 INTERIM ANALYSIS

Interim analyses, covering all planned final analyses up to the interim data cut date, will be conducted at the time points indicated below:

- Following full enrollment and completion of the 12-week treatment duration with 40, 80, or 160 mg PLN-74809 (completion of Parts 1 and 2).
- Following full enrollment and completion of the 12-week treatment duration with 320 mg PLN-74809 (Part 3)

Blinding measures for interim analyses performed on data up to Week 12 for all participants in Part 3 will be described in a separate blinding plan. Briefly, every effort will be taken to maintain the blind in the required blinded portion of the trial. The analysis and interpretation of interim results will be conducted by a separate unblinding team who are not involved in the ongoing study conduct. The blinding plan will describe the membership and level of data access of the unblinded and blinded teams and appropriate documentation process in the suspected unintentional unblinding of a blinded team member. Blinded team members will not have access to individual treatment assignment or individual study results. Aggregate results will be presented to Sponsor management.

Interim data from Part 3 will include all assessments up to the Week 12 assessments, [REDACTED]. Adverse events or concomitant medications started/initiated [REDACTED] will not be summarized in the interim analysis and will be presented in the final analysis. Participants who discontinue treatment or the study post the Week 12 assessment date [REDACTED] will be summarized as on treatment/on study for the purposes of the interim analyses.

Confidentiality Statement

This document [REDACTED] may not be duplicated, copied, altered or removed from company [REDACTED] without prior approval [REDACTED].

Controlled Quality Management Document		
	Sponsor:	Pitant Therapeutics Inc.
	Protocol Number:	PLN-74809-PSC-203

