1 INTRODUCTION

This document details the planned statistical analyses for Pliant Therapeutics Inc. Study PLN-74809-PSC-203, “A randomized, double-blind, dose-ranging, placebo-controlled, Phase 2a evaluation of the safety, tolerability, and pharmacokinetics of PLN-74809 in participants with primary sclerosing cholangitis (PSC) and suspected liver fibrosis (INTEGRIS-PSC)”.

The proposed analyses are based on the contents of the [REDACTED]

[REDACTED]

This is a Phase 2a, multicenter, 3-part, randomized, double-blind, dose-ranging, placebo-controlled study to evaluate the safety, tolerability, and PK of once-daily (QD) treatment with PLN-74809 in male and female participants aged 18 to 75 years with an established diagnosis of large duct PSC and suspected liver fibrosis. Part 1 will evaluate 40 mg PLN-74809 and placebo, Part 2 will evaluate 80 and 160 mg PLN-74809 and placebo and Part 3 will evaluate 320 mg PLN-74809 and placebo. Placebo participants will be pooled across the study when comparing to PLN-74809 treatment groups.

Each study part will include an up to 42-day screening period, followed by a treatment period of either 12 weeks (Parts 1 and 2) or at least 24 weeks and up to 48 weeks (Part 3), and finally a 4-week post-treatment follow-up period. Based on regulatory considerations, randomization to dose level in Part 2 of the protocol (80 or 160 mg PLN-74809) was conducted in either parallel or sequential manner.

Each participant in Parts 1 and 2 will participate in the study for approximately 154 days (22 weeks), including screening, treatment, and post-treatment safety follow-up. The duration for Part 3 of the study will be variable depending on the study enrollment rate. The duration of participation will be approximately 238 days (34 weeks) for the last participant enrolled and approximately 406 days (58 weeks) for the first participant enrolled including screening, treatment, and post-treatment safety follow-up. The end of Part 3 will commence once the last participant reaches 24 weeks of treatment. At that time, all study participants will complete their next scheduled visit (End of Treatment [EOT]) and the 4 weeks of follow up (End of Study [EOS]). The end of study is defined as the last visit of the last participating participant.

Confidentiality Statement

This document [REDACTED] may not be duplicated, copied, altered or removed from company [REDACTED]
without prior approval [REDACTED]

	Controlled Quality Management Document	

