6.11 Pooled Placebo

Participants in the placebo group will be pooled across study Parts for summaries and comparison to PLN-74809 treatment groups.

--	--

Controlled Quality Management Document

Sponsor:	Pliant Therapeutics Inc.
----------	--------------------------

Protocol Number:	PLN-74809-PSC-203
------------------	-------------------

STATISTICAL ANALYSIS PLAN**Confidentiality Statement**

This document [REDACTED] may not be duplicated, copied, altered or removed from company [REDACTED] without prior approval [REDACTED].

Controlled Quality Management Document

Sponsor:

Pliant Therapeutics Inc.

Protocol Number:

PLN-74809-PSC-203

STATISTICAL ANALYSIS PLAN**6.12 Baseline and Clinical Characteristics**

Baseline summaries will be presented by treatment group (PLN-74809 dose (40, 80, 160 or 320 mg, All PLN-74809) or Placebo) and overall (PLN-74809 dose and Placebo) for the following variables based on the safety population:

Demographic Data

- Age at informed consent (years)
- Sex
- Ethnicity
- Race, where more than 1 race is selected the participant will be presented under the 'Multiple races' category in the summary but each selected race will be displayed in the listing.

Baseline Characteristics

- Weight at Screening (kg)
- Height at Screening (cm)
- BMI at Screening (kg/m²)
- Fertility status (childbearing potential, postmenopausal, surgically sterile)

Clinical Characteristics

- Duration since diagnosis at baseline (defined as the number of months from start date of first date reported for medical history preferred term "Cholangitis sclerosing" to first dose)
- Use of UDCA (Yes/no)
- Duration of UDCA usage at baseline (defined as the number of months from start date of UDCA to first dose)
- Partial Mayo Score for IBD (for participants with IBD ongoing at screening)

■ [REDACTED]

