6.20 Adverse Events

AE analyses will be presented by the actual treatment received for the Safety Population.

[REDACTED]

AEs will be collected from the time of informed consent through completion of the participant's last study visit.

A treatment-emergent adverse event (TEAE) is defined as:

- Any AE that has an onset on or after the first dose of study drug through completion of the last study visit.
- Any pre-existing AE that has worsened in severity on or after the first dose of study drug through completion of the last study visit.

AEs occurring prior to first dose of study drug are considered non-treatment emergent and will be listed only.

The Investigator will determine the relationship of the AE to treatment (related, not related). If an AE has missing relationship it is assumed to be related to the study drug for analysis purposes.

Severity of the AE will be graded using the Common Terminology Criteria for Adverse Events (CTCAE) grading system (Version 5.0): Grade 1 (mild), Grade 2 (moderate), Grade 3 (severe), Grade 4 (life-threatening), Grade 5 (fatal). Grade 3 (severe) will be assumed for an AE with missing grade.

An overall summary of AEs (number of participants with an event) will be presented by treatment group and overall, for the following:

- TEAE

[REDACTED]

[REDACTED]

Controlled Quality Management Document

Sponsor: Pliant Therapeutics Inc.

Protocol Number: PLN-74809-PSC-203

STATISTICAL ANALYSIS PLAN

Confidentiality Statement

This document [REDACTED] may not be duplicated, copied, altered or removed from company
without prior approval [REDACTED].

Controlled Quality Management Document

Sponsor:

Pliant Therapeutics Inc.

Protocol Number:

PLN-74809-PSC-203

STATISTICAL ANALYSIS PLAN

- TEAE related to study drug
- TEAE Related to a Study Procedure
- Serious TEAE
- Serious TEAE Related to Study Drug
- TEAE of CTCAE Grade 3 or Higher
- TEAE of CTCAE Grade 3 or Higher Related to Study Drug
- TEAE Leading to Interruption of Study Drug
- TEAE Leading to Withdrawal of Study Drug
- TEAE Leading to Early Termination from Study
- TEAE Leading to Death

Summaries of TEAEs (number of participants with an event) will be presented by system organ class and preferred term by treatment group for the following:

- TEAE
- TEAE Related to Study Drug
- Serious TEAE
- Serious TEAE Related to Study Drug
- TEAE Related to a Study Procedure
- TEAE of CTCAE Grade 3 or Higher
- TEAE of CTCAE Grade 3 or Higher Related to Study Drug

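### The readable text cuts only Part 3 at Week 12 for the Part 3 interim, so crude TEAE incidence can compare 12 weeks of 320 mg with 15 to 16 weeks in the other columns

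*SAP*

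**What the plan says.** Section 7 plans "Interim analyses, covering all planned final analyses up to the interim data cut date". The first follows 12 weeks of treatment with 40, 80 or 160 mg and is described as "completion of Parts 1 and 2". The second follows 12 weeks of treatment with 320 mg in Part 3.

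For the second look, "Interim data from Part 3 will include all assessments up to the Week 12 assessments"; the rest of that sentence is redacted. Adverse events and concomitant medications that start beyond a redacted cut-off "will not be summarized in the interim analysis and will be presented in the final analysis". Participants who stop treatment or leave the study after the Week 12 assessment "will be summarized as on treatment/on study for the purposes of the interim analyses".

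Section 6.20 defines a TEAE as "Any AE that has an onset on or after the first dose of study drug through completion of the last study visit", or a pre-existing event that worsens in the same window. Section 1 gives Parts 1 and 2 a 12-week treatment period, "and finally a 4-week post-treatment follow-up period".

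Section 6.11 says "Participants in the placebo group will be pooled across study Parts for summaries and comparison to PLN-74809 treatment groups". Section 6.8.5 shows all four doses and placebo side by side. Section 6.8.3 bases adverse event percentages on the number of participants in the group.

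**The concern.** TEAE incidence is the primary safety endpoint (Section 3.1). It is cumulative: the longer the counting window, the more participants have at least one event. With participants as the denominator and no exposure adjustment in the readable text, two columns are comparable only if their windows match.

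On the readable rules they do not match at the Part 3 interim. The 320 mg column stops at Week 12, while the 40, 80 and 160 mg columns and most of the placebo column run on through the off-treatment follow-up. Other counts with a start but no stated end have the same problem: treatment-emergent laboratory abnormalities (Section 6.20.2) and concomitant medications (Section 6.14). For ALP, Table 1 in Section 6.18 schedules an off-treatment Week 16 sample in Parts 1 and 2, so there is a real extra opportunity to record an abnormality.

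This interim is the planned Week 12 look at the highest dose, and its aggregate results go to sponsor management. Any distortion makes 320 mg look relatively better than the other columns. Showing the later events in the final analysis does not change what was read at the interim.

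**Working it through.** **Plan figures reproduced.** Section 5 gives 21 active and 7 placebo for each of four doses: 4 × (21 + 7) = 112, as stated. Participation in Parts 1 and 2 is 42 + 84 + 28 = 154 days, as stated in Section 1. The sample size was set empirically, so there is no power calculation to reproduce.

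**Windows at the Part 3 interim.** This assumes no dropout, that Parts 1 and 2 have finished follow-up by then, and that only Part 3 is cut.

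| Column | Participants | Window | Person-weeks |
|---|---|---|---|
| 320 mg | 21 | 12 weeks | 21 × 12 = 252 |
| 40, 80, 160 mg (each) | 21 | 12 + 4 = 16 weeks | 21 × 16 = 336 |
| Pooled placebo | 21 from Parts 1/2, 7 from Part 3 | 16 and 12 weeks | 21 × 16 + 7 × 12 = 420 |

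The placebo average is 420 / 28 = 15 weeks.

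**Size of the artefact.** The SAP gives no event rate, so this part rests on assumptions. Let p12 be the 12-week incidence, with the same true constant hazard on treatment in every group, and let r be the off-treatment hazard divided by the on-treatment hazard. Then:

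- p16 = 1 − (1 − p12)^(1 + r/3), because 4 weeks is one third of 12
- pooled placebo = (21 × p16 + 7 × p12) / 28

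Example with r = 1 and p12 = 40%: p16 = 1 − 0.6^(4/3) = 49.4%, and placebo = 0.75 × 49.4% + 0.25 × 40% = 47.0%. So 320 mg reads 9.4 points below each lower dose and 7.0 below placebo, with no true difference.

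| p12 | r = 1: vs other doses | r = 1: vs placebo | r = 0.5: vs other doses | r = 0.5: vs placebo |
|---|---|---|---|---|
| 10% | −3.1 | −2.3 | −1.6 | −1.2 |
| 20% | −5.7 | −4.3 | −2.9 | −2.2 |
| 40% | −9.4 | −7.0 | −4.9 | −3.7 |
| 58% | −10.5 | −7.9 | −5.7 | −4.2 |
| 70% | −9.9 | −7.4 | −5.5 | −4.1 |
| 90% | −5.4 | −4.0 | −3.2 | −2.4 |

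At r = 0 every entry is 0. At r = 1 the maximum falls near p12 = 58%.

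**What could be masked.** At r = 1, a true hazard ratio of 320 mg to placebo equal to ln(1 − placebo incidence) / ln(1 − p12) would show as equal incidence. That ratio is 1.25 at p12 = 10%, 1.24 at 40% and 1.24 at 70%.

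**With a common cut.** Every column has 12 weeks (320 mg 252 person-weeks, placebo 28 × 12 = 336), and the artefact is 0 at equal hazards.

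**The case against.** The strongest reply is that the cut-off is redacted where it is defined. The adverse event sentence is not itself limited to Part 3 in its readable words; only the sentence before it names Part 3. A cut covering all Parts cannot be excluded. Section 6.18.1 also mentions a Week 12 interim for Parts 1, 2 and 3, but it concerns biomarkers and does not set the adverse event window. The rule on later discontinuations fits only Part 3, since treatment in Parts 1 and 2 has ended by Week 12. The Part 3 reading is therefore the natural one, but it remains an inference.

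A reader might go further and infer that the interim makes 320 mg look safer than it is, or that its later events are lost. The SAP does not support either. Time on treatment is matched at 12 weeks, the 320 mg figure is a proper 12-week incidence, and later events are deferred to the final analysis. Only the side-by-side comparison is affected, and only through first events that start in off-treatment follow-up.

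It is also fair that the tables are descriptive, that Section 7 states no decision rule for TEAEs, and that DSMB reporting is separate. Chance variation is larger than the artefact: at 59.5% of 21 against 67.4% of 28, the standard error is √(0.595 × 0.405/21 + 0.674 × 0.326/28), about 14 points. The artefact is a shift in expectation, not a prediction of what one table will show. By-visit laboratory and vital sign summaries compare like visits, and treatment discontinuation is not mismatched.

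What remains is that the SAP counts follow-up events as TEAEs, and the readable rules give the columns unequal windows.

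**Conclusion.** The point holds in a limited form. As far as the text can be read, the Part 3 Week 12 interim compares a 12-week window for 320 mg with 16 weeks for the other doses and 15 on average for pooled placebo. If so, the expected shift favours 320 mg whenever any first events start in follow-up, because extra counting time can only add participants with events.

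Its size is a range that starts at zero. With equal true hazards, it is at most about 4 points against placebo and 6 against the other doses at half the on-treatment hazard, and at most about 8 and 10.5 points at equal hazard. These figures rest on a constant hazard, no dropout, completed follow-up in Parts 1 and 2, and an off-treatment hazard that the SAP does not give.

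The effect is confined to this interim and to cumulative counts: TEAEs, treatment-emergent laboratory abnormalities, concomitant medications and study withdrawal. It is a cheap improvement, not a flaw that invalidates the analysis.

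**What to change.** Unless the redacted wording already does this, add one sentence to Section 7: at the Part 3 Week 12 interim, the same Week 12 cut, with the same day rule, applies to Parts 1 and 2, active and placebo, for TEAEs, treatment-emergent laboratory abnormalities, concomitant medications and study withdrawal. Tabulate the Weeks 12 to 16 follow-up events of Parts 1 and 2 separately, and keep the full-window tables for the final analysis. If the redacted words already cover all Parts, confirming that is enough.

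The cost is one sentence, one date filter in the interim programs and one extra table, with no new data. Section 6 already provides for an addendum if the SAP has been approved. Counts for Parts 1 and 2 can come out slightly lower than in the earlier Parts 1 and 2 interim, so a footnote should say why.

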8 DATA AND SAFETY MONITORING BOARD ANALYSIS

Data and safety monitoring board (DSMB) analyses [REDACTED] will be performed by an external vendor. All DSMB related reporting are detailed in the DSMB Charter.

9 CHANGES TO PLANNED PROTOCOL ANALYSIS

The following additions or revisions to protocol specified analyses are included in this SAP:

Confidentiality Statement
This document [REDACTED] may not be duplicated, copied, altered or removed from company [REDACTED]
without prior approval [REDACTED]

Controlled Quality Management Document

Sponsor: Pliant Therapeutics Inc.

[figure not shown]
Protocol Number: PLN-74809-PSC-203

STATISTICAL ANALYSIS PLAN

Confidentiality Statement

[figure not shown]
This document [REDACTED] may not be duplicated, copied, altered or removed from company [REDACTED]
without prior approval [REDACTED]

Controlled Quality Management Document	
	Sponsor: Pliant Therapeutics Inc.
	Protocol Number: PLN-74809-PSC-203
STATISTICAL ANALYSIS PLAN	

Confidentiality Statement	
This document [REDACTED] without prior approval	[REDACTED] may not be duplicated, copied, altered or removed from company [REDACTED]

Controlled Quality Management Document	
	Sponsor: Pliant Therapeutics Inc.
	Protocol Number: PLN-74809-PSC-203
STATISTICAL ANALYSIS PLAN	

[figure not shown]
Confidentiality Statement	
This document [REDACTED] without prior approval	[REDACTED] may not be duplicated, copied, altered or removed from company [REDACTED]

Controlled Quality Management Document	
	Sponsor: Pliant Therapeutics Inc.
	Protocol Number: PLN-74809-PSC-203
STATISTICAL ANALYSIS PLAN	

[figure not shown]
[figure not shown]
Confidentiality Statement	
This document [REDACTED] without prior approval	[REDACTED] may not be duplicated, copied, altered or removed from company [REDACTED]

Controlled Quality Management Document	
Sponsor:	Pliant Therapeutics Inc.
Protocol Number:	PLN-74809-PSC-203
STATISTICAL ANALYSIS PLAN	

[figure not shown]
Confidentiality Statement	
This document [REDACTED] without prior approval	[REDACTED] may not be duplicated, copied, altered or removed from company [REDACTED]

Controlled Quality Management Document	
Sponsor:	Pliant Therapeutics Inc.
Protocol Number:	PLN-74809-PSC-203
STATISTICAL ANALYSIS PLAN	

[figure not shown]
[figure not shown]
Confidentiality Statement	
This document [REDACTED] without prior approval	[REDACTED] may not be duplicated, copied, altered or removed from company [REDACTED]

Controlled Quality Management Document	
Sponsor:	Pliant Therapeutics Inc.
Protocol Number:	PLN-74809-PSC-203
STATISTICAL ANALYSIS PLAN	

[figure not shown]
Confidentiality Statement	
